8.4 Response Criteria for Control/Relieve/Eliminate Endpoints

8.4.1. *Measurable soft-tissue lesions*

When evaluating soft-tissue lesions, the definitions in Table 3 apply.

Table 3 RECIST response criteria for target (soft-tissue) lesions

Response	Evaluation of Soft-Tissue Lesions
Complete response (CR)	Disappearance of all target lesions. Any pathological lymph nodes (whether target or non-target) must have reduction in short axis to <10 mm.
Partial response (PR)	At least a 30% decrease in the sum of diameters of target lesions, taking as reference the baseline sum diameters.
Progressive disease (PD)	At least a 20% increase in the sum of diameters of target lesions, taking as reference the smallest sum on study (this includes the baseline sum if that is the smallest on study). In addition to the relative increase of 20%, the sum must also demonstrate an absolute increase of at least 5 mm. (Note: the appearance of one or more new lesions is also considered progression).
Stable disease (SD)	Neither sufficient shrinkage to qualify for PR nor sufficient increase to qualify for PD, taking as reference the smallest sum diameters while on study.

Abbreviations: LD, longest diameter.

In some circumstances, it may be difficult to distinguish residual disease from normal tissue. When the evaluation of complete response depends on this determination, it is recommended that the residual lesion be investigated (e.g., fine needle aspirate or biopsy) before confirming the complete response status.

Changes in nodal and visceral sites should be recorded and reported separately, and lymph nodes in the pelvis must measure at least 2 cm in greatest diameter to be considered target lesions. Complete elimination of disease at a particular site

Radium-223

MSKCC

PCCTC LOI: c13-124

IRB#: 14-098 A (5)

should be recorded separately. Any favorable change should be confirmed using a second follow-up scan.

8.4.2 *PSA*

As long as patient safety is the primary concern, in the absence of other indicators of disease progression, therapy should not be discontinued solely on the basis of a rise in PSA.

For each patient, use a waterfall plot to report the percent change in PSA from baseline to 12 weeks (or earlier for those who discontinue therapy) and the maximum decline in PSA that occurs at any point after treatment.

8.4.3 *Bone*

Record the number of post-treatment lesions. In the absence of clearly worsening soft-tissue (nodal and visceral) disease or disease-related symptoms, progression at the first scheduled assessment should be confirmed on a second scan performed at least 6 weeks later. In the rare case where *visible lesions disappear, this too should be confirmed.*

8.4.4 *Non-target lesions*

When assessing non-target lesions, the definitions in Table 4 will apply.

Table 4 RECIST response criteria for non-target lesions

Response	Evaluation of Non-target Lesions
Complete response (CR)	The disappearance of all non-target lesions and normalization of tumor marker levels. All lymph nodes must be non-pathological in size (<10 mm short axis).
Incomplete response/ stable disease (SD)	The persistence of one or more non-target lesions and/or maintenance of tumor marker levels above the normal limits
Progressive disease (PD)	The appearance of one or more new lesions and/or unequivocal progression of existing non-target lesions

A clear progression of non-target lesions only is exceptional.

8.4.5 *Symptoms*

BPI short form used to assess pain which includes change in BPI pain severity index, BPI functional interference index. Fatigue based on the BFI will also be used.

8.5 Confirmatory Measures/Duration of Response

8.5.1 *Confirming time-to-event outcomes*

Any posttreatment change in disease status, be it favorable or unfavorable, should be confirmed using a second assessment at a later time point not less than 6 weeks later.

8.5.2 *Duration of overall response*

Duration of overall response is measured from the time when partial response or complete response is first noted until the date when recurrent or progressive

Radium-223

MSKCC

PCCTC LOI: c13-124

IRB#: 14-098 A (5)

disease is objectively documented. Duration of overall complete response is measured from the time the criteria for complete response are first met until the first date that recurrent disease is objectively documented. Duration of stable disease is measured from the start of treatment until the criteria for progression are met.

8.5.3 *Progression-free survival*

Progression-free survival (PFS) is a composite endpoint defined as the time from study entry or random assignment to disease progression in bone or soft-tissue, symptoms, or death. Use an interval-censored approach in which all assessments of the composite PFS endpoint (i.e., PSA, bone, CT scans, and symptom assessments) are performed at the same time points. All assessments of disease should be collected at the same time interval (e.g., bone scan, CT scan, and PSA at 12-week intervals). In addition to PSA, confirm posttreatment changes in measurable target lesions, radionuclide bone scans, and symptoms.

Table 6 Prostate Cancer Clinical Trials Working Group Outcome Measures⁵

Variable	Control/Relieve/Eliminate Endpoints
PSA	Record the percent change from baseline (rise or fall) at 12 weeks and, separately, the maximal change (rise or fall) at any time using a waterfall plot
Soft-tissue lesions	
Use RECIST with caveats:
 
Record changes in nodal and visceral soft tissue sites separately
 
Record complete elimination of disease at any site separately
 
Confirm favorable change with second scan
 
Record changes using waterfall plot

Bone	
Record outcome as either new lesions or no new lesions
 
First scheduled reassessment:
 
No new lesions: continue therapy
 
2 new lesions: perform a confirmatory scan at least 6 weeks later
 
Confirmatory scan of first reassessment:
 
No new lesions: continue therapy
 
2 additional new lesions: progression
 
Subsequent scheduled reassessments:
 
No new lesions: continue therapy
 
2 new lesions: continue therapy and perform a confirmatory scan at least 6 weeks later
 
Confirmatory scan of subsequent reassessments:
 
Lack of persistence of the previously observed new lesions: continue therapy
 
Persistence of or an increase in the number of new lesions: progression

Symptoms	
Consider independently of other outcome measures
 
Document pain and analgesia at entry with a lead-in period and measure repeatedly at 3- to 4-week intervals
 
Ignore early changes (~12 weeks) in pain or HRQOL in absence of compelling evidence of disease progression
 
Confirm response or progression of pain or HRQOL endpoints ~3 weeks later

Abbreviations: PSA, prostate-specific antigen; HRQOL, health-related quality of life. †Particularly important when anticipated effect on PSA is delayed or for biologic therapies.

9. DATA REPORTING AND REGULATORY REQUIREMENTS

9.1 Data Collection and Management

Data collected during this study will be entered into a secure database.

9.1.1 *Electronic Case Report Forms (eCRFs)*

The participating sites will enter data remotely into electronic Case Report Forms (eCRFs) using the internet based PCCTC Casis Electronic Data Capture (EDC) system. Completion Guidelines will be created by the PCCTC for the collection of all study data. Access and training for PCCTC Casis EDC will be made available to participating sites upon local regulatory approval. The participating site PI is responsible for ensuring eCRFs are completed accurately and in a timely manner.

9.1.2 *Source documents*

Source documentation refers to original records of observations, clinical findings and evaluations that are subsequently recorded as data. Source documentation will be made available to support the subject's research record.

9.1.3 *Record retention*

The investigator will maintain adequate and accurate records to enable the conduct of the study to be fully documented and the study data to be subsequently verified. The investigator will ensure that all regulatory documents and participating site IRB correspondences are maintained in an onsite regulatory binder. After study closure, the investigator will maintain all source documents and study-related documents.. Records are to be retained and securely stored until the later of: (a) two (2) years following the date a New Drug Application is approved for the Study Drug that is the subject of the Clinical Trial; or (b) two (2) years after the Investigational New Drug Application for such Study Drug is terminated or withdrawn, or such longer period of time as may be required by Participant policies, applicable laws, rules or regulations.

9.1.4 *Source Documentation Submission for Registration at Participating Sites*

Participating sites should email any source documentation that corresponds to data entered at registration to PCCTC at [contact] within 24 hours (see Section 4.2.1).

9.1.5 *Data Submission Timelines*

All study data should be transmitted to PCCTC within 14 days of visit except for SAE submission (see Section 8.3.1) as described in the Data Management Plan.

9.1.6 *Data Review and Queries*

PCCTC will review data and source documentation as it is submitted. Data will be monitored and source data verified as necessary and discrepancies will be sent as queries to the participating sites. In addition, PCCTC will review data for logic, consistency, and obvious anomalies. Queries will be sent by PCCTC to participating sites as needed.

Participating sites should respond to data queries within 14 days of receipt.

9.2 Study Monitoring and Quality Assurance

9.2.1 *Data and Safety Monitoring*

Radium-223

MSKCC

PCCTC LOI: c13-124

IRB#: 14-098 A (5)

The Data and Safety Monitoring Plans (DSMP) at Memorial Sloan-Kettering Cancer Center were approved by the National Cancer Institute in September 2001. The plans address the new policies set forth by the NCI in the document entitled "Policy of the National Cancer Institute for Data and Safety Monitoring of Clinical Trials" which can be found at: <http://www.cancer.gov/clinicaltrials/conducting/dsm-guidelines/page1>. The DSMPs at MSKCC were established and are monitored by the Office of Clinical Research. The MSKCC DSMPs can be found on the MSKCC Intranet at: <http://inside2/clinresearch/Documents/MSKCC%20Data%20and%20Safety%20Monitoring%20Plans.pdf>.

There are several different mechanisms by which clinical trials are monitored for data, safety, and quality. There are institutional processes in place for quality assurance (e.g., protocol monitoring, compliance and data verification audits, therapeutic response, and staff education on clinical research quality assurance) and departmental procedures for quality control, plus there are two institutional committees that are responsible for monitoring the activities of our clinical trials programs. There are several committees: Data and Safety Monitoring Committee (DSMC) for Phase I and II clinical trials, and the Data and Safety Monitoring Board (DSMB) for Phase III clinical trials, report to the MSKCC Research Council and Institutional Review Board. As a moderate risk trial, this study will be monitored by DSMC twice per year.

Since therapeutic efficacy is a stated primary objective, all sites participant's responses are subject to review by MSKCC's Therapeutic Response Review Committee (TRRC). Radiology and additional lab reports will need to be obtained from the participating sites for MSKCC TRRC review and confirmation of response assessment. These materials must be sent to MSKCC promptly upon request

9.2.2 *Data Auditing and Quality Assurance*

In addition to review by DSMC, PCCTC will conduct regularly scheduled remote monitoring every 6 weeks and audits as specified below. Registration reports will be generated by the PCCTC to monitor subject accruals and the completeness of registration data. Routine data quality reports will be generated to assess missing data and inconsistencies. Accrual rates and the extent and accuracy of evaluations and follow-up will be monitored periodically throughout the study period, and potential problems will be brought to the attention of the Principal Investigator for discussion and action.

Each site participating in the accrual of participants to this protocol will be audited at a minimum of 10% of all subjects, but at least 2 from each site will be 100% source data verified by the PCCTC. Auditing will occur once shortly after initiation of subject recruitment at a site, annually during the study (or more frequently if indicated), and at the end or closeout of the trial, for protocol and regulatory compliance, data verification and source documentation. Audits may be accomplished in one of two ways: (1) sending source documents and research

Radium-223

MSKCC

PCCTC LOI: c13-124

IRB#: 14-098 A (5)

records for selected patients from participating sites to the PCCTC for audit, or
(2) on-site auditing of selected patient records at participating sites.

The audit will include a review of source documentation to evaluate compliance for:

- Regulatory/IRB compliance (review of current protocol and amendments, Informed consent documents and procedures, annual continuing review reports, AEs/SAEs)
- Protocol defined treatment compliance
- Subject records
 1. Each subject is reviewed to determine that there is a signed and dated consent form
 2. Adherence to eligibility criteria
 3. Baseline, on study and follow-up protocol testing
 4. eCRF completion

Audit findings will be reviewed and disseminated to the site PIs and staff.

In addition, each participating site accruing participants to this protocol will be audited by MSK for protocol and regulatory compliance, data verification and source documentation. Audits of selected participant records may be conducted on-site or remotely.

Audits will be conducted annually at minimum, and more often if significant and/or repeated findings are identified during monitoring visits. The number of participants audited will be determined by the outcome of monitoring visits and complexity of the protocol.

Each audit will be summarized and a final report will be sent to the PI at the audited participating site within 30 days of the audit. The report will include a summary of findings, participant-specific case review, recommendations on any performance and/or shortcomings and request for corrective action, when necessary. When corrective action is required, the participating site must reply within 45 days of receipt of the audit report with their corrective action plan.

10. STATISTICAL CONSIDERATIONS

10.1 Study Endpoints

10.1.1 *Analysis of the primary endpoint*

The primary objective of this phase II study is to determine the effect of Radium-223 on pain improvement for patients with symptomatic metastatic castration-resistant disease. The primary endpoint of the study is a 30% decline in the BPI worst pain item from baseline to week 8, with a confirmed reduction at week 12 without an escalation of the subject's pain regimen from Step 1 to Step 2 or Step 2 to Step 3 of the WHO analgesic ladder. The baseline BPI worst pain score average will be based on the worst pain scores completed by the patient in the 7 consecutive pretreatment days. A minimum of 4 days of pain scores must be completed by the patient in the 7

day window in order to calculate the average worst pain score. We define this event as a response and propose declaring the treatment effective if the probability of a response in the population exceeds 0.20.

A maximum of 63 patients will be entered onto the study. A two-stage design that differentiates between response rates of 0.20 and 0.35 will be used to assess treatment efficacy. In the first stage of the study 27 patients will be enrolled. If at most 5 patients respond, accrual will be terminated. If at least 6 patients respond, an additional 36 patients will be entered onto the study. At the conclusion of this second stage, if at least 17/63 patients respond, the treatment will be declared effective. The probability of declaring the treatment effective is 0.10 when the response rate in the population is 0.20 and increases to 0.90 when the response rate is 0.35.

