8.3 Therapeutic Response

Response and progression will be evaluated in this study using a combination of the revised

Radium-223

MSKCC

PCCTC LOI: c13-124

IRB#: 14-098 A (5)

international criteria proposed by the Response Evaluation Criteria in Solid Tumors (RECIST 1.1) committee and the guidelines for prostate cancer endpoints developed by the Prostate Cancer Clinical Trials Working Group (PCWG2).

Trial objectives are defined based on controlling, relieving, or eliminating disease manifestations that are present when treatment is initiated. Traditional measures of response reflect when a treatment is working and measures of progression indicate when a drug should be stopped. Because assessing response in bone (the most common site of prostate cancer spread) is uncertain and the clinical significance of PSA changes in response to therapy is not a reliable predictor of response, measures of response have been expanded in consortium trials to include measures of progression.

Patients will need to be reevaluated for response every 12 weeks \pm 1 week during protocol therapy according to the guidelines below.

8.3.1 *PSA*

Perform PSA testing at a minimum of 1-week intervals with the threshold PSA level at 2.0 ng/mL To report PSA-based outcomes, PCWG2 recommends that the percent of change in PSA from baseline to 12 weeks (or earlier for those who discontinue therapy) and the maximum decline in PSA that occurs at any point after treatment be reported for each patient using a waterfall plot. Because declines in serum PSA, if they occur, may not do so for several weeks, PSA measurements obtained during the first 12 weeks should not be used as the sole criterion for clinical decision making.

8.3.2 *Measurable disease*

According to RECIST 1.1, measurable disease is defined as at least 1 lesion \geq 10 mm in its longest diameter as measured with conventional techniques (i.e., CT or MRI). To be considered pathologically enlarged and measurable, a lymph node must be \geq 15 mm in short axis when assessed by CT scan. All tumor measurements will be taken using a ruler or calipers and recorded in millimeters (or decimal fractions of centimeters).

8.3.3 *Nonmeasurable disease*

Following RECIST 1.1, all other lesions (or sites of disease) will be considered nonmeasurable disease. This includes small lesions (longest diameter $<$ 10 mm or pathological lymph nodes with \geq 10 to $<$ 15mm short axis) and any of the following:

- Bone lesions
- Ascites

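### Do the general confirmation rules in Section 8.5 undercut the week 8 / week 12 primary pain endpoint?

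*Combined protocol and SAP*

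**What the plan says.** The primary endpoint, in Section 10.1.1 and in matching terms in the synopsis, 8.1 and 10.2.1, is "a 30% decline in the BPI worst pain item from baseline to week 8, with a confirmed reduction at week 12", without escalation on the WHO ladder. The schema note in the synopsis describes the same thing as a week 8 pain response confirmed at week 12. The count of such responders decides whether accrual continues (at least 6 of 27) and whether the treatment is declared effective (at least 17 of 63).

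Section 8.5 carries general confirmation text:

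- 8.5.1, headed as concerning time-to-event outcomes, says of disease status that a change seen after treatment, "be it favorable or unfavorable, should be confirmed using a second assessment at a later time point not less than 6 weeks later".
- 8.5.3, on progression-free survival, says to "confirm posttreatment changes in measurable target lesions, radionuclide bone scans, and symptoms".
- The outcome-measures table in 8.5.3 has a Symptoms row. It treats symptoms separately from the other outcomes and asks for pain to be measured every 3 to 4 weeks. It then says "Ignore early changes (~12 weeks) in pain or HRQOL in absence of compelling evidence of disease progression". On the confirmation interval, the same row says "Confirm response or progression of pain or HRQOL endpoints ~3 weeks later".

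Section 8.3 brings RECIST 1.1 and the PCWG2 guidelines into the study ("Response and progression will be evaluated in this study using a combination of the revised" international criteria and those guidelines), and 8.4.5 lists pain among the response criteria ("BPI short form used to assess pain which includes change in BPI pain severity index"). Section 9.2.1 makes responses at all sites subject to "MSKCC TRRC review and confirmation of response assessment".

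**The concern.** Section 8.5 is where a reader looks for the rule on confirming a change, and its 6-week minimum is longer than the interval built into the primary endpoint. Taken at face value, 8.5.1 means a week 8 response can never be confirmed at week 12. The early-change line in the table seems to set aside the two time points that decide the trial. Nothing in the document says which text governs.

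The responder count drives both decisions, and a review committee also looks at responses. If two people applied different confirmation rules, they could reach different counts. A stricter rule would lower the counted response rate and therefore the power.

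**Working it through.** **1. The plan's own figures.** Inputs from 10.1.1: 27 patients in stage 1, continue with at least 6 responders, 36 more patients, success with at least 17 of 63. For a true response rate p,

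P(effective) = Σ over x = 6 to 27 of C(27, x) p^x (1−p)^(27−x) × P(Bin(36, p) ≥ 17 − x).

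| p | P(stop at stage 1) | P(declare effective) | Stated |
|---|---|---|---|
| 0.20 | 0.539 | 0.0999 | 0.10 |
| 0.35 | 0.051 | 0.902 | 0.90 |

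The stated figures are reproduced. They depend on p and the cut-offs only. The confirmation interval enters only through what counts as a response.

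**2. The interval.** Week 8 to week 12 is 4 weeks, or 28 days. The 8.5.1 minimum is 6 × 7 = 42 days. If the ±3-day visit window of Section 5.2 applied at both ends, the gap would be 28 ± 6 = 22 to 34 days; with the ±7-day window of Section 5.5, 28 ± 14 = 14 to 42 days. So 8.5.1 would practically never be met. These windows are stated for clinic visits, not for the 7-day home reporting periods, so the ranges are indicative. The first scheduled pain assessment at least 42 days after week 8 is week 16 (56 days), or week 24 (112 days) under the schema's 12-weekly note.

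**3. Which rule reaches pain response?** The confirmation intervals in the document are:

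| Outcome | Interval | Where |
|---|---|---|
| Primary pain response | 4 weeks (week 8 to week 12) | Synopsis, 8.1, 10.1.1, 10.2.1 |
| Pain response or progression, general | about 3 weeks | 8.5.3 table, Symptoms |
| Pain progression | 2 weeks, or 4 weeks | Synopsis and 10.2.1; 8.2 |
| PSA progression after a decline | 3 weeks or more | Synopsis, 8.2 |
| Imaging progression | 6 weeks or more | 8.3.5, 8.3.7, 8.4.3 |
| Change in disease status | 6 weeks or more | 8.5.1 |

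The 6-week figure in 8.5.1 is the imaging interval. If it overrode endpoint definitions, it would also void the PSA and pain-progression definitions, although time to pain progression is itself a time-to-event outcome. The document therefore lets the specific definition stand over 8.5.1. The only general rule in 8.5 that sets an interval for pain is about 3 weeks, and 4 weeks meets it.

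**4. The early-change line.** It applies when there is no compelling evidence of progression, and it sits in a general table within a section on progression-free survival. That section mentions random assignment although the trial has one arm, and progression-free survival is not an endpoint in 8.2. The line reads most naturally as a caution against calling progression on early symptoms. It does not withdraw a response defined in advance at named weeks.

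**5. What a later confirmation would do.** This is illustration only, because the document gives no figure for how many week 8 / week 12 responders still respond at week 16. Assume a week 8 / week 12 rate of 0.35 and a share of responders lost by the later assessment:

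| Assumed share lost | Counted rate | P(declare effective) |
|---|---|---|
| 0% | 0.35 | 0.902 |
| 5% | 0.35 × 0.95 = 0.3325 | 0.849 |
| 10% | 0.35 × 0.90 = 0.315 | 0.776 |
| 20% | 0.35 × 0.80 = 0.28 | 0.575 |
| 30% | 0.35 × 0.70 = 0.245 | 0.337 |

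The interval would matter if someone changed it. Under the endpoint as written, the first row applies.

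**The case for a change.** The strongest case for acting is that the sentence in 8.5.1 is wide. It covers favorable changes, 8.4.5 puts pain among the response criteria, and 8.5.3 asks for symptom changes to be confirmed. The heading of 8.5.1 does nothing to soften the early-change line, which as printed still reaches week 8; a pain responder would usually show no compelling progression, so the qualifier offers little shelter. Section 1.2.1 quotes a mean pain relief of 44 days at the two higher doses, which lies between 28 and 56 days. A couple of exempting sentences would cost almost nothing.

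Part of this stands. The general text was not reconciled with the trial's endpoint, and the early-change line fits poorly beside a week 8 assessment. The rest carries less weight. The 44 days followed a single injection, whereas here doses are scheduled at weeks 1, 5, 9 and 13, so it says little about persistence in this trial. For the committee review, 9.2.1 names radiology and laboratory reports, not pain scores or analgesic diaries, and nothing there points to 8.5.1 as the rule for pain. An exemption would be tidy, but it would leave every count where it already is.

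Whether the week 12 reduction must again reach 30% is a separate question of definition, independent of Section 8.5. The schema note already implies that it must.

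**Conclusion.** No change is needed. Section 8.5 holds general working-group text that was left untrimmed, and the mismatch with the primary endpoint is clerical. The week 8 / week 12 definition is explicit, repeated consistently, and placed in the sections that define the primary analysis and the responders. It also agrees with the only general confirmation interval in 8.5 that is specific to pain. Analysts following 8.1 and 10.1.1 reach sound decisions at 6/27 and 17/63, with exact error and power of 0.0999 and 0.902. The effect on results is nil.

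This rests on the endpoint-specific definition being applied at both looks, which is how the document already treats PSA and pain progression. The power losses shown for a later confirmation depend on assumed shares and describe a rule that the plan does not adopt.
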